8.3.2 Definition of Serious Adverse Event (SAE)

An AE or suspected adverse reaction is considered serious (i.e., is an SAE) if, in the view of either the investigator or the Sponsor, it results in any of the following outcomes:

- Death;
- A life-threatening AE;
- Inpatient hospitalization or prolongation of existing hospitalization;
- A persistent or significant incapacity or substantial disruption of the ability to conduct normal life functions; or
- A congenital anomaly/birth defect.

Important medical events that may not meet the above criteria may be considered serious when, based upon appropriate medical judgment, they may jeopardize the subject and may require medical or surgical intervention to prevent one of the outcomes listed in this definition. Examples of such medical events include allergic bronchospasm requiring intensive treatment in an emergency room or at home, blood dyscrasias, convulsions that do not result in inpatient hospitalization, or the development of drug dependency or drug abuse.

“Life-threatening” refers to an AE that at occurrence represents an immediate risk of death to a subject. An event that may cause death if it occurs in a more severe form is not considered life-threatening. Similarly, a hospital admission for an elective procedure is not considered a SAE.

All SAEs, as with any AE, will be assessed for severity and relationship to study intervention.

All SAEs will be recorded on the SAE CRF.

All SAEs will be followed through resolution or stabilization by a licensed study physician (for IND studies, a physician listed on the Form FDA 1572 as the site PI or Sub-Investigator).

All SAEs will be reviewed and evaluated by DMID and will be sent to the DSMB (for periodic review), and the IRB/IEC.

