8.3.4.1 Severity of Adverse Events

All AEs and SAEs will be assessed for severity using the DAIDS Table for Grading the Severity of Adult and Pediatric Adverse Events, version 2.1 (July 2017).

For AEs not included in the Table, the following guidelines will be used to describe severity. In addition, all deaths related to an AE are to be classified as grade 5 according to the DAIDS Table.

- Moderate (Grade 2): Events that are usually alleviated with additional specific therapeutic intervention. The event interferes with usual activities of daily living and causes discomfort, but poses no significant or permanent risk of harm to the research subject.
- Severe (Grade 3): Events that interrupt usual activities of daily living, or significantly affect clinical status, or may require intensive therapeutic intervention. Severe events are usually incapacitating.
- Severe (Grade 4): Events that are potentially life threatening.
- Deaths (Grade 5): All deaths related to an AE are to be classified as grade 5. (per DAIDS Table).

AEs characterized as intermittent require documentation of onset and duration of each episode. The start and stop dates (duration) of each reported AE will be recorded on the appropriate CRF. Changes in the severity of an AE will be documented to allow an assessment of the duration of the event at each level of intensity.

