3. STUDY OBJECTIVES AND ENDPOINTS

3.1. Study Objectives

Primary Objective

The overall objective of the study is to evaluate the clinical efficacy of different investigational therapeutics relative to the control arm in patients hospitalized with COVID-19 as assessed by the time to recovery up to Day 29.

Secondary Objectives

The key secondary objective is to evaluate the clinical efficacy of different investigational therapeutics relative to the control arm in patients hospitalized with COVID-19 as assessed by the 8-point ordinal clinical status scale at Day 15.

The other secondary objectives are to:

1. Evaluate clinical efficacy of different investigational therapeutics as compared to the control arm as assessed by:
 - Clinical Severity
 - 8-Point Clinical Status Ordinal scale:
 - Time to an improvement of one category and two categories from Day 1 (baseline) on the clinical status 8-point ordinal scale.
 - Subject clinical status using 8-point ordinal scale at Days 3, 5, 8, 11, 15, 22, and 29.
 - Mean change in the clinical status 8-point ordinal scale from Day 1 to Days 3, 5, 8, 11, 15, and 29.
 - National Early Warning Score (NEWS):
 - Time to discharge or to a NEWS of ≤ 2 and maintained for 24 hours, whichever occurs first.
 - Change from Day 1 to Days 3, 5, 8, 11, 15, and 29 in NEWS.
 - Oxygenation:
 - Days requiring oxygen through Day 29.
 - Incidence and duration of new oxygen use through Day 29.
 - Non-invasive ventilation/high flow oxygen:
 - Days of non-invasive ventilation/high flow oxygen through Day 29.
 - Incidence and duration of new non-invasive ventilation or high flow oxygen use through Day 29.
 - Invasive Mechanical Ventilation / extracorporeal membrane oxygenation (ECMO):
 - Days of ventilator/ECMO through Day 29.

- Incidence and duration of new mechanical ventilation or ECMO use through Day 29.
 - Hospitalization
 - Duration of hospitalization (in days) through Day 29.
 - Mortality
 - 14-day mortality.
 - 28-day mortality.
2. Evaluate the safety of the intervention through 28 days of follow-up as compared to the control arm as assessed by:
- Cumulative incidence of SAEs through Day 29
 - Cumulative incidence of Grade 3 and 4 clinical and/or laboratory AEs through Day 29.
 - Discontinuation or temporary suspension of infusions (for any reason).

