9.4. Deaths, Serious Adverse Events and other Significant Adverse Events

A listing of death and other serious adverse events will be presented, including Subject ID, treatment group, Adverse Event Description, Associated Dose Number, Number of Days Post Dose (Duration), Number of Days Post Dose the Event Became Serious, Reason Reported as an SAE, Severity, Relationship to Treatment, Alternate Etiology if not Related, Action Taken with

Study Treatment, Subject Discontinuation, Outcome, MedDRA SOC, and MedDRA PT (Listing 12 and Listing 13).

The number of subjects who die by Day 15 and Day 29 will be presented by treatment arm. The 14- and 28-day crude mortality rate, which will use the number of subjects in the treatment group and analysis population as the denominator, will be presented (Table 59). The analysis will be repeated censoring placebo subjects who were retreated with remdesivir at the time of retreatment.

Mortality through Day 15 and 29 will also be analyzed as a time to event endpoint (see Section 3.3). A table will present median time to event along with 95% confidence intervals overall for each treatment arm along with the hazard ratio estimate and log rank p-values (Table 61). Differences in time-to-event endpoints by treatment will be summarized with Kaplan-Meier curves (Figure 23). Analyses of mortality will be performed in the ITT and the Treated analysis populations and will be performed on both the early and the full analysis sets.

The ITT tabular summaries will be repeated censoring placebo subjects who were retreated with remdesivir at the time of retreatment. Similarly, the summaries will be repeated censoring subjects who were unblinded at the time of unblinding.

Rates of Grade 3 and 4 AE occurrence will be compared between treatment arms using Barnard's exact test and presented (Table 63). Rates of SAE occurrence will also be compared between treatment arms using Barnard's exact test and presented. Further, the composite endpoint of the occurrence of death, SAE, or Grade 3 or 4 AE described in Section 3.3 will be analyzed as a time to event outcome. A table will present median time to event along with 95% confidence intervals overall for each treatment arm along with the hazard ratio estimate and log rank p-values (Table 64). Differences in time-to-event endpoints by treatment will be summarized with Kaplan-Meier curves (Figure 24).

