Programming Notes: The “Analysis Population” column will be replaced by a column titled “Unblinding/Crossover Remdesivir Treatment”. The first set of summaries will be for the “Unblinding” sensitivity analyses, and the second set will be for the “Crossover Remdesivir Treatment” sensitivity analyses.

Table 61: Time to Death through Day 15 and 29 by Treatment Group

Analysis Population	Study Day	Treatment Group	Median Time			HR		P-value
			n	Estimate	95% CI	Estimate	95% CI	
ITT Population	Day 15	Remdesivir (N=X)	x	x.x	x.x, x.x	x.x	x.x, x.x	x.xxx
		Placebo (N=X)	x	x.x	x.x, x.x			
	Day 29	Remdesivir (N=X)	x	x.x	x.x, x.x	x.x	x.x, x.x	x.xxx
		Placebo (N=X)	x	x.x	x.x, x.x			
Treated Population	Day 15	Remdesivir (N=X)	x	x.x	x.x, x.x	x.x	x.x, x.x	x.xxx
		Placebo (N=X)	x	x.x	x.x, x.x			
	Day 29	Remdesivir (N=X)	x	x.x	x.x, x.x	x.x	x.x, x.x	x.xxx
		Placebo (N=X)	x	x.x	x.x, x.x			

N= Number of subjects in the specified treatment group and analysis population.
n = Number of subjects who died by the specified study day.
HR is the hazard ratio from the Cox Model
P-value calculated using the Log-rank test

Table with similar format:

Table 62: Time to Death through Day 15 and 29 by Treatment Group – Unblinding and Crossover Treatment Sensitivity Analysis

Programming Notes: The “Analysis Population” column will be replaced by a column titled “Unblinding/Crossover Remdesivir Treatment”. The first set of summaries will be for the “Unblinding” sensitivity analyses, and the second set will be for the “Crossover Remdesivir Treatment” sensitivity analyses.

Table 63: Subjects Experiencing Grade 3 or 4 AEs and SAEs through Day 29 by Treatment Group– Treated Population

Safety Event Outcome	Remdesivir (N=X)			Placebo (N=X)			P-value
	n	%	95% CI	n	%	95% CI	
Grade 3 or 4 AE	x	x	x.x, x.x	x	x	x.x, x.x	0.xxx
SAE	x	x	x.x, x.x	x	x	x.x, x.x	0.xxx

N = Number of Subject in the Treated Population.
n = Number of subjects in a given treatment group who experienced the specified safety event outcome.
95% CI calculated using C-P/Blaker method
P-value calculated using Barnard's Exact Test

Table 64: Analysis of Time to Death, SAEs, or Grade 3 or 4 AEs by Treatment Group – Treated Population

Treatment Group	n	Median Time		HR		P-value
		Estimate	95% CI	Estimate	95% CI	
Remdesivir (N=X)	x	x.x	x.x, x.x	x.x	x.x, x.x	x.xxx
Placebo (N=X)	x	x.x	x.x, x.x			

N= Number of subjects in the Treated Population.

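### The Grade 3 or 4 AE row of SAP Table 63 leaves out subjects whose only AE record is Grade 5, so that one comparison leans towards the arm with more deaths

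*SAP*

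**What the plan says.** SAP 9.4 states that "Rates of Grade 3 and 4 AE occurrence will be compared between treatment arms", using Barnard's exact test. The shell is Table 63, titled "Subjects Experiencing Grade 3 or 4 AEs and SAEs through Day 29 by Treatment Group". It has two tested rows, one for Grade 3 or 4 AEs and one for SAEs. The objective behind the first row, in SAP 3.1, is "Cumulative incidence of Grade 3 and 4 clinical and/or laboratory AEs through Day 29". SAP 9.3 sets the denominator for AE incidence as the Treated population.

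Protocol 8.3.4.1 says that "all deaths related to an AE are to be classified as grade 5 according to the DAIDS Table". SAP Table 57 lists Grade 3, Grade 4 and Grade 5 (death) on separate lines, so the SAP treats them as distinct values.

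Other safety comparisons are also tested:
- SAP 9.4 continues: "Rates of SAE occurrence will also be compared between treatment arms". Protocol 8.3.2 calls an AE serious when "it results in any of the following outcomes", and death heads that list.
- SAP 9.4 analyses "the composite endpoint of the occurrence of death, SAE, or Grade 3 or 4 AE" as a time-to-event outcome with a log-rank p-value (Table 64).
- SAP 9.4 also analyses mortality through Day 15 and Day 29, with hazard ratios and log-rank p-values (Table 61).

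**The concern.** The grading rule and the counting rule do not meet. A fatal AE is Grade 5, the row counts Grades 3 and 4, and nothing in either document says that Grade 5 belongs in it.

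Subjects with only a Grade 5 record are plausible. Protocol 8.3.5.1 asks sites to group clearly related signs, symptoms and test results under a single diagnosis. Protocol 9.4.4 counts each AE once per subject. Fatal respiratory failure and its severe components may therefore become one record, graded 5.

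Such a subject has had the worst possible outcome, yet the row treats them like a subject with no severe AE. The number lost this way rises with the number of deaths. A treatment that turned fatal events into survivable Grade 4 events would show more events in this row. The row is a named secondary safety objective with its own reported p-value, in a disease where deaths are expected.

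**Working it through.** **Figures in the plan.** The documents give no rate, sample size or power for this comparison. The figures borrowed here do reproduce:
- Total N (Protocol 9): 400 recoveries / 0.70 = 571.4, so 572, or 286 per arm at 1:1.
- Day 15 deaths (Protocol Tables 5 and 7, odds ratio 1.75). For control 2%: odds 0.02/0.98 = 0.02041; divided by 1.75 = 0.01166; probability 0.01166/1.01166 = 1.15% (Table 7: 1.2%). For control 3%: 0.03093/1.75 = 0.01767, giving 1.74% (Table 7: 1.7%).

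**Model.** Let g be the proportion with any Grade 3, 4 or 5 AE, d the death rate, and f the share of deaths with no countable Grade 3 or 4 record. The row then shows g − f·d in each arm. With g and f equal in both arms, the spurious difference (treatment minus control) is

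f × (d_control − d_treatment).

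The value of g cancels from the difference and matters only for the test.

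**Assumptions.** g = 30% in both arms; f from 0 to 1; death rates of 10% v 6% and 15% v 9% to represent higher mortality by Day 29. None of these is in the documents.

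**Chance that treatment looks significantly worse.** This uses a pooled two-proportion test at two-sided 0.05 with n = 286 per arm, as a normal approximation to the planned exact test:

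1 − Φ[(1.96·se0 − difference)/se1], with se0 = √(2p̄(1−p̄)/n) and se1 = √(p_c(1−p_c)/n + p_t(1−p_t)/n).

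Example, deaths 10% v 6%, f = 0.5:
- Control: 30 − 0.5×10 = 25%. Treatment: 30 − 0.5×6 = 27%. Difference: 2 points.
- se0 = √(2×0.26×0.74/286) = 0.0367, and se1 is 0.0367 to the same precision.
- (1.96×0.0367 − 0.02)/0.0367 = 1.415, so the chance is 7.9%. With no distortion it is 2.5%.

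| Deaths, control v treatment | f | Row, control v treatment | Difference (points) | Chance treatment looks significantly worse |
|---|---|---|---|---|
| 2% v 1.15% (plan, anticipated) | 0.5 | 29.00% v 29.43% | 0.43 | 3.2% |
| 2% v 1.15% | 1 | 28.00% v 28.85% | 0.85 | 4.1% |
| 3% v 1.74% (plan, most severe) | 0.5 | 28.50% v 29.13% | 0.63 | 3.6% |
| 3% v 1.74% | 1 | 27.00% v 28.26% | 1.26 | 5.2% |
| 10% v 6% (assumed) | 0.25 | 27.5% v 28.5% | 1.0 | 4.5% |
| 10% v 6% | 0.5 | 25% v 27% | 2.0 | 7.9% |
| 10% v 6% | 1 | 20% v 24% | 4.0 | 21% |
| 15% v 9% (assumed) | 0.5 | 22.5% v 25.5% | 3.0 | 13% |
| 15% v 9% | 1 | 15% v 21% | 6.0 | 46% |

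Barnard's test on the rounded expected counts gives p = 0.67 for 10% v 6% at f = 0.5 (72 v 77 subjects). In the last line of the table (43 v 60) it gives p = 0.068.

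**After the fix.** Counting Grades 3, 4 and 5 gives 30% v 30% throughout: difference 0, chance 2.5%.

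**The case against.** The strongest reply is that deaths are not lost from the safety evaluation. Protocol 9.4.4 deliberately lists death, SAEs and Grade 3 and 4 AEs as separate endpoints, to be analysed singly and as a composite, and SAP 9.4 follows it. A subject whose only event is fatal is an event in the next row of the same table, in the composite and in the mortality analyses. This stands, and it limits the harm. It does not repair the row, whose estimate and p-value are reported separately and answer a question about grade rather than seriousness.

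A second reply is that f may be well below 1. Protocol 8.3.4.1 also asks that changes in an AE's severity be documented, so a fatal AE may carry an earlier Grade 4 phase, and a dying inpatient may well have another Grade 3 or 4 AE. Table 63 counts subjects who experienced the outcome and does not restrict to final grade. This also stands as a reason for a small f. But no rule says that an earlier phase of a fatal AE counts, so two programmers could reach different totals.

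Third, the documents' own planning death rates give little distortion. That is correct. Those rates are for Day 15, though, and Protocol 9.2 itself calls the assumptions behind them highly uncertain, while Table 63 runs to Day 29.

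A reader might infer that this row is the trial's only test of severe harm, so that a fatal case passes as event-free in the safety evaluation as a whole. The documents do not support that: the SAE, composite and mortality tests all count the death.

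**Conclusion.** The point holds for one row of one table. As worded, the Grade 3 or 4 AE comparison omits subjects whose only AE record is Grade 5 while keeping them in the denominator. If f is similar in the two arms, this favours the arm with more deaths.

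The size is f × (difference in death rates). At the anticipated and most severe planning scenarios for Day 15 it is at most about 0.9 and 1.3 points, and about 0.4 and 0.6 points at f = 0.5. It reaches 2 points or more only with higher mortality than the plan assumed, for example 10% v 6% with f = 0.5. Neither f nor the Grade 3 to 5 rate is given, so the larger figures are illustrations. The calculated chances depend on 286 per arm; a given bias would show more readily at the 600 to over 800 subjects the protocol also mentions.

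The SAE row, the composite, the mortality analyses, the primary analysis and the sample size are unaffected. The change is still worth making, because the stated rule gives a misleading count in a tested secondary safety comparison and is almost free to correct.

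**What to change.** In SAP 9.4 and Table 63, count subjects with an AE of Grade 3 or higher (3, 4 or 5), once per subject at maximum grade. Alternatively, keep the protocol-worded row and add this one beside it. Because SAP 2.1 says version 3.0 was written after the interim results were known, adding the row is the more transparent course. If the existing row stays, state whether an earlier Grade 3 or 4 phase of a fatal AE counts in it.

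Align the endpoint wording in SAP 3.1 and in Protocol sections 3 and 9.4.4, so that protocol and SAP do not diverge. The composite already includes death, so its result does not change. The Grade 3, 4 and 5 split in Table 57 can stay.

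The cost is a small wording change and one programming condition. Deaths and SAEs are already collected through Day 29, so no new data are needed. The downside is some overlap with the SAE row.

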9.5. Pregnancies

For any subjects in the Treated population who become pregnant during the study, every attempt will be made to follow these subjects to completion of pregnancy to document the outcome, including information regarding any complications with pregnancy and/or delivery. Note that the CSR will not be delayed to wait for outcomes of any pregnancies; an addendum to the CSR would be provided in such a scenario. A set of listings of pregnancies and outcomes will be presented (Listing 14, Listing 15, Listing 16, Listing 17, Listing 18).

9.6. Clinical Laboratory Evaluations

Clinical safety laboratory adverse events are collected Day 1, 3, 5, 8, 11 and Day 15 and 29 if able to return to clinic or still hospitalized. Parameters evaluated include white blood cell count, absolute neutrophil count, eGFR, platelet count, hemoglobin concentration, creatinine, glucose, total bilirubin, ALT, AST, and PT/INR. Laboratory safety parameters will be graded according to the Division of AIDS (DAIDS) Table for Grading the Severity of Adult and Pediatric Adverse Events, version 2.1 (July 2017).

The distribution of Grade 3 and 4 chemistry and hematology laboratory results by maximum severity, time point, disease severity and treatment group will be presented (Table 65).

Descriptive statistics including mean, median, standard deviation, maximum, and minimum values and change from baseline by time point, for all and each chemistry and hematology laboratory parameter will be summarized by disease severity and treatment arm (Table 66). Changes in chemistry and hematology laboratory values will be presented in line graphs over time with mean and SD plotted by disease severity and treatment arm (Figure 25).

Listings will provide a complete listing of individual chemistry and hematology laboratory results with applicable reference ranges (Listing 19).

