⁷ In-person visits are preferred but recognizing quarantine and other factors may limit the subject's ability to return to the site for the visit. In this case, the visit may be performed by phone.

- If still hospitalized at Day 15 and 29 or returns to the site for an in-person visit: Clinical data, vital signs, safety laboratory tests, and research laboratory samples (OP swab and serum only) as able.
- If phone call only on Days 15 and 29 and all Day 22 visits: assess adverse events, clinical status (ordinal scale), readmission to a hospital, and mortality only.

⁸ Oropharyngeal swabs are preferred, but if these are not obtainable, nasopharyngeal swabs may be substituted.

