9. STATISTICAL CONSIDERATIONS

This study is intended to allow for two types of adaptations: 1) sample size re-estimation and 2) addition of new experimental arm(s). A brief summary is provided here. Details will be described in the statistical analysis plan (SAP).

Sample size re-estimation: The target of 400 recoveries corresponds to a total sample size that depends on the proportion of subjects who recover by Day 29. This proportion will be evaluated on pooled (i.e., blinded) data to evaluate the total sample size required. A preliminary estimate based on a 70% recovery probability is 572 patients.

Addition of new experimental therapies: If additional data become available to add an experimental therapy, the sample size will be updated accordingly. Analyses of newly added arm(s) will be performed comparing concurrently enrolled control subjects. This approach was used in the recent PALM study in patients with Ebola virus disease [Mulangu 2019]. Principles of adding arms and addressing questions of “when, what and how” to add them will be developed to guide the study team in their decision-making and will be outlined in a document on interim monitoring.

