3.2. Endpoints

Primary Endpoint

Time to recovery, where recovery is defined as clinical status in states 1, 2, or 3 of the 8-point ordinal scale, censored at Day 29.

- Clinical status of a subject (8-point ordinal scale) is defined below:
 - 8. Death;
 - 7. Hospitalized, on invasive mechanical ventilation or ECMO;
 - 6. Hospitalized, on non-invasive ventilation or high flow oxygen devices;
 - 5. Hospitalized, requiring supplemental oxygen;

4. Hospitalized, not requiring supplemental oxygen - requiring ongoing medical care (COVID-19 related or otherwise);
3. Hospitalized, not requiring supplemental oxygen - no longer requiring ongoing medical care;
2. Not hospitalized, limitation on activities and/or requiring home oxygen;
1. Not hospitalized, no limitations on activities

Secondary Endpoints

The key secondary endpoint is clinical status (8-point ordinal scale) on Day 15.

The other secondary endpoints are:

- Ordinal outcome assessed daily while hospitalized and on Days 15, 22, and 29.
- NEWS assessed daily while hospitalized and on Days 15 and 29.
- Days of supplemental oxygen (if applicable).
- Days of non-invasive ventilation/high-flow oxygen (if applicable).
- Days of invasive mechanical ventilation/ECMO (if applicable).
- Days of hospitalization.
- Date and cause of death (if applicable).
- SAEs.
- Grade 3 and 4 adverse events
- WBC with differential, hemoglobin, platelets, creatinine, glucose, total bilirubin, ALT, AST, and PT on Day 1; Days 3, 5, 8, and 11 (while hospitalized); and Days 15 and 29 (if attends in-person visit or still hospitalized).

Exploratory Endpoint

- Qualitative and quantitative polymerase chain reaction PCR for SARS-CoV-2 in OP swab on Day 1; Days 3, 5, 8, and 11 (while hospitalized); and Days 15 and 29 (if attends in-person visit or still hospitalized).
- Qualitative and quantitative PCR for SARS-CoV-2 in blood on Day 1; Days 3, 5, 8, and 11 (while hospitalized).

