6. GENERAL STATISTICAL CONSIDERATIONS

6.1. General Principles

This is a double-blind, placebo controlled randomized trial with a two-sided type I error rate of 0.05. Secondary hypotheses have been ordered according to relative importance. These will be described according to the appropriate summary statistics, e.g.

- Percentages/proportions/odds ratios for categorical data. For tabular summaries of percentages/proportions, the denominator (e.g. number of subjects with non-missing data) will be displayed.
- Means, median, and range for continuous data, median for time-to-event data.

Confidence intervals will be generated; for the primary analysis, the confidence level will take into account the group-sequential design of the trial (see Section 6.6 and Section 8.1) whereas 95% confidence intervals will be generated for secondary and exploratory outcomes. For hazard ratio and odds ratio estimates, Wald confidence intervals will be used. For other efficacy outcomes, Wilson or Score confidence intervals will be used. For safety outcomes, exact (e.g. Clopper-Pearson) confidence intervals will be used.

When calculating treatment effects (e.g. differences, hazard ratios, odds ratios) and when using treatment arm as a covariate in regression modeling, the placebo arm will be used as the reference group. For regression modeling that uses strata variables defined in Section 6.4, the first stratum listed for each variable in that section will be used as the reference group.

For the final time-to-event analyses, the following SAS pseudocode will be used to perform stratified analyses to generate stratum-specific median time to event estimates and confidence intervals, stratum-specific Kaplan-Meier curves, and to perform the log-rank test. For any unstratified analyses, code can be used after the removal of the `strata ... ;` line.

```
proc lifetest data=dataset plots=(s);
  time TimeVariable * CensorVariable(1);
  strata StrataVariable;
  test TreatmentVariable;
run;
```

Note that the interim efficacy analyses will be performed using R. For all interim and final analyses, the software used will calculate the log rank statistic using the formula in Section 8.1.1.

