n = Number of subjects who died or experienced SAEs, Grade 3 or 4 AEs, or Discontinuation of Study Infusions.

HR is the hazard ratio from the Cox Model

P-value calculated using the Log-rank test

Table 65: Abnormal Laboratory Results of Grade 3 or 4 by Parameter, Maximum Severity, Time Point, and Treatment Group – Treated Population

Laboratory Parameter	Time Point	Treatment Group	N	Severe/ Grade 3		Life Threatening/ Grade 4	
				n	%	n	%
Any Parameter	Baseline	Remdesivir	x	x	x	x	x
		Placebo	x	x	x	x	x
	Day 3	Remdesivir	x	x	x	x	x
		Placebo	x	x	x	x	x
	Day 5	Remdesivir	x	x	x	x	x
		Placebo	x	x	x	x	x
	Day 8	Remdesivir	x	x	x	x	x
		Placebo	x	x	x	x	x
	Day 11	Remdesivir	x	x	x	x	x
		Placebo	x	x	x	x	x
	Day 15	Remdesivir	x	x	x	x	x
		Placebo	x	x	x	x	x
	Day 29	Remdesivir	x	x	x	x	x
		Placebo	x	x	x	x	x
	Maximum Severity Post Baseline	Remdesivir	x	x	x	x	x
		Placebo	x	x	x	x	x

Each parameter will be summarized individually similar to the above...

The “Max Post Baseline” rows indicate the maximum severity experienced by each subject at any time point post baseline, including unscheduled assessments.

N = Number of subjects in the Treated Population

Table 66: Summary Statistics of Laboratory Results by Parameter, Study Visit Day, and Treatment Group – Treated Population

Laboratory Parameter	Study Visit Day	Treatment Group	Absolute					Change from Baseline				
			N	Mean	SD	Median	Min, Max	N	Mean	SD	Median	Min, Max
Parameter 1	Baseline	Remdesivir	x	xx.x	xx.x	xx.x	xx.x, xx.x	---	---	---	---	---
		Placebo	x	xx.x	xx.x	xx.x	xx.x, xx.x	---	---	---	---	---
	Day 3	Remdesivir	x	xx.x	xx.x	xx.x	xx.x, xx.x	x	xx.x	xx.x	xx.x	xx.x, xx.x
		Placebo	x	xx.x	xx.x	xx.x	xx.x, xx.x	x	xx.x	xx.x	xx.x	xx.x, xx.x
	Day 5	Remdesivir	x	xx.x	xx.x	xx.x	xx.x, xx.x	x	xx.x	xx.x	xx.x	xx.x, xx.x
		Placebo	x	xx.x	xx.x	xx.x	xx.x, xx.x	x	xx.x	xx.x	xx.x	xx.x, xx.x
	Day 8	Remdesivir	x	xx.x	xx.x	xx.x	xx.x, xx.x	x	xx.x	xx.x	xx.x	xx.x, xx.x
		Placebo	x	xx.x	xx.x	xx.x	xx.x, xx.x	x	xx.x	xx.x	xx.x	xx.x, xx.x
	Day 11	Remdesivir	x	xx.x	xx.x	xx.x	xx.x, xx.x	x	xx.x	xx.x	xx.x	xx.x, xx.x
		Placebo	x	xx.x	xx.x	xx.x	xx.x, xx.x	x	xx.x	xx.x	xx.x	xx.x, xx.x
	Day 15	Remdesivir	x	xx.x	xx.x	xx.x	xx.x, xx.x	x	xx.x	xx.x	xx.x	xx.x, xx.x
		Placebo	x	xx.x	xx.x	xx.x	xx.x, xx.x	x	xx.x	xx.x	xx.x	xx.x, xx.x
	Day 29	Remdesivir	x	xx.x	xx.x	xx.x	xx.x, xx.x	x	xx.x	xx.x	xx.x	xx.x, xx.x
		Placebo	x	xx.x	xx.x	xx.x	xx.x, xx.x	x	xx.x	xx.x	xx.x	xx.x, xx.x

Continue for all parameters...

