N = Number of subjects in the Treated Population with laboratory data available for the parameter at the specified study visit.

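### The footnote to SAP Table 65 gives every by-visit row the whole Treated Population as N, so subjects not tested at a visit count as non-cases; the dilution is small, descriptive and cheap to remove

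*SAP*

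**What the plan says.** SAP 9.6 assigns to Table 65 "The distribution of Grade 3 and 4 chemistry and hematology laboratory results by maximum severity", along with time point, disease severity and arm. Table 65 in SAP Appendix 1 has rows for Baseline, Days 3, 5, 8, 11, 15 and 29, and maximum severity after baseline. Each row has N, n and % by arm, first for an 'Any Parameter' block and then for each parameter. Its only definition of N is "N = Number of subjects in the Treated Population". SAP 6.3.1 makes that population everyone who received any infusion, whatever visits they attended. The shell does not say how the percentage is formed.

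The next shell, Table 66, uses the same laboratory data and is narrower: "N = Number of subjects in the Treated Population with laboratory data available for the parameter at the specified study visit".

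Testing is conditional. SAP 3.2 sets it for Day 1 and then "Days 3, 5, 8, and 11 (while hospitalized); and Days 15 and 29 (if attends in-person visit or still hospitalized"). Note 7 to the protocol's schedule of assessments (1.2) shows that phone visits carry no laboratory tests: "If phone call only on Days 15 and 29 and all Day 22 visits: assess adverse events, clinical status (ordinal scale"), readmission and mortality only.

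On percentages in general, SAP 6.1 says that "the denominator (e.g. number of subjects with non-missing data) will be displayed".

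**The concern.** On a post-baseline row, the Treated Population is not the set of subjects who could have had a result. If % is n divided by the footnoted N, a discharged subject who was not tested stays in the denominator as a non-case. The printed figure is then the share tested multiplied by the rate among those tested. If remdesivir shortens the stay, as the trial hypothesizes, its share tested falls faster and its percentage is diluted more. The distortion favours remdesivir in a safety table.

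Protocol 2.3.2 names transaminase elevation as a remdesivir risk, and Table 65 is the only by-arm table of graded results by visit. The adverse event tables cover part of the question. Table 63 pools all Grade 3 and 4 events, Table 58 lists only terms that reach 5%, and protocol 8.3.5.1 has a laboratory abnormality that belongs to a syndrome recorded as the syndrome.

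**Working it through.** **Inputs from the documents.** Pooled recovery by Day 29 is 70% (Protocol 9: "A preliminary estimate based on a 70% recovery probability is 572 patients"). The recovery rate ratio is 1.35 (Protocol 9.2, SAP 5). With 1:1 allocation, 572/2 = 286 per arm.

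**Assumptions.** Recovery is exponential and equals discharge; all hospitalized subjects are tested; Grade 3/4 risk among tested subjects is equal in the two arms; deaths are not modelled.

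**Planning figures first.** E = 4(1.96 + 1.036)²/{ln 1.35}² = 35.91/0.0901 ≈ 399, against 400 stated. 400/0.70 = 571.4, which agrees with 572.

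**Formula.** Let s be the share of an arm tested at a visit and r the Grade 3/4 rate among those tested. The literal percentage is s × r. With equal r, the remdesivir/placebo ratio is s_R/s_P, where 1.00 is correct among tested subjects.

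**Hazard.** Solve ½[(1 − e^(−28h)) + (1 − e^(−28 × 1.35h))] = 0.70, which gives h = 0.0371 per day. With t = d − 1, s_P = e^(−ht) and s_R = e^(−1.35ht).

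**Variant with no discharge in the first 3 days.** Exclusion 4 bars subjects expected to be discharged within 72 hours. Starting discharge at t = 3 and keeping 70% pooled recovery gives h = 0.0371 × 28/25 = 0.0415, applied to t − 3.

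| Visit | s_P v s_R, from Day 1 | Ratio | Ratio, 3-day delay |
|---|---|---|---|
| Day 3 | 0.928 v 0.905 | 0.97 | 1.00 |
| Day 5 | 0.862 v 0.818 | 0.95 | 0.99 |
| Day 8 | 0.771 v 0.704 | 0.91 | 0.94 |
| Day 11 | 0.690 v 0.606 | 0.88 | 0.90 |
| Day 15, no in-person returns | 0.595 v 0.496 | 0.83 | 0.85 |

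**In-person returns.** If a share q of discharged subjects is tested in person, the share tested is s + q(1 − s). On Day 15 without the delay, q = 0.25 gives 0.696 v 0.622 (0.89), q = 0.5 gives 0.797 v 0.748 (0.94), and q = 1 gives 1.00. On Day 29 the ratios are 0.70, 0.84, 0.92 and 1.00 for q = 0, 0.25, 0.5 and 1. The documents give no value for q.

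**What the table would print.** On Day 11 without the delay, 286 × 0.690 = 197 placebo and 286 × 0.606 = 173 remdesivir subjects are tested. If 10% of tested subjects in each arm are affected (assumed), the literal values are 6.1% remdesivir and 6.9% placebo. SAP 13 rounds percentages to whole numbers, so the table shows 6% v 7%. A true 12% v 10% becomes 7.3% v 6.9% and prints as 7% v 7%. With the 3-day delay, 10% in both arms becomes 6.8% v 7.5% before rounding.

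**Sensitivity.**
- Over pooled recovery of 60% to 80% and rate ratio 1.25 to 1.40, without the delay, the Day 11 ratio runs from 0.93 to 0.82, and Day 15 with no returns from 0.90 to 0.76.
- If 12.5% of recovered subjects stay in hospital and are tested (score 3 in Scenario 1: 10/(10 + 30 + 40)), Day 11 is 0.90 and Day 15 is 0.87.
- The plan's separate Day 15 ordinal Scenario 1, with odds ratio 1.75, has 28.0% of control and 18.5% of treated subjects alive in hospital. The ratio is 0.66 with no returns and 0.93 with half returning.
- With equal discharge rates both arms are diluted equally and the ratio is 1.00.

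**The case against.** **This is an ambiguous shell, and the SAP's own example points the other way.** Table 65 never states % = n/N, and SAP 6.1 illustrates a denominator with non-missing subjects. Tables 61 and 64 put a fixed population N in the row label, whereas Table 65 has a separate N column on each row, as Table 66 does. A programmer might well use the number tested. That is fair, but 6.1 offers only an example, and the footnote is the specific instruction. Table 66 has the same column and writes the restriction out; Table 65 does not. A sponsor who intends tested-only percentages still needs to correct the footnote.

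**A reader might infer that the number tested is hidden.** It is not. Table 66 prints it for each parameter, visit and arm, and Listing 19 gives each result with its grade. Only the 'Any Parameter' block lacks a tested count.

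**A reader might infer that liver toxicity would go unseen or be understated.** The documents do not support this. ALT and AST each have a row said to "indicate the maximum severity experienced by each subject at any time point post baseline, including unscheduled assessments", and Table 66 and Figure 25 give laboratory values by visit and arm. Whether the literal percentages understate toxicity depends on subjects who were not tested. If none of them had a Grade 3 or 4 result, the figures would be right per treated subject.

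**The largest ratios rest on extreme cases.** The Day 15 and Day 29 values of 0.83 and 0.70 need no in-person returns, although both documents prefer in-person visits. The arm difference also needs remdesivir to speed discharge. This stands. Unmodelled deaths could add to the effect or offset it.

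**Conclusion.** The point holds as a minor one. As footnoted, Table 65's by-visit percentages are not rates among tested subjects, they disagree with the adjacent table's definition, and they are diluted more in the arm that leaves hospital sooner. Under the stated assumptions the between-arm distortion is near zero on Day 3, 10% to 12% on Day 11, and on Day 15 15% to 17% with no in-person returns or 6% with half returning. After rounding this is often one percentage point or nothing visible, although rounding can also make a real difference look equal.

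The rows are descriptive: no test, error rate, sample size or stopping decision uses them. The point does not extend to the maximum post-baseline row or to the adverse event tables, where the Treated Population is a conventional denominator.

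**What to change.** - In the by-visit rows of Table 65, define N as in Table 66. For 'Any Parameter', use Treated subjects with at least one graded parameter at that visit. State % = n/N.
- Keep the Treated Population as denominator in the maximum post-baseline row, and show there how many subjects had any post-baseline result.
- Add a footnote that the by-visit rows are descriptive and cover only subjects still in hospital or seen in person.

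The cost is a revised footnote, one denominator in the table program and one added count. No new data are needed, since Table 66 already requires the per-parameter N. The downside is that tested-only percentages compare groups selected after randomization. If less ill subjects leave sooner on remdesivir, those still tested in that arm may be sicker, which is why the descriptive label is needed.
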